### 7.3 Adverse Event Surveillance

Safety monitoring will take place throughout the study. Events that are reported by participants without prompting will also be captured and followed.

All study procedures will take place during the initial visit, under the supervision of the Principal Investigator. The Principal Investigator is a physician and all visits will take place at a clinical facility, allowing for clinical intervention if needed. The risks associated with the study are immediate; that is, it is considered highly unlikely that a related adverse event will take place after the completion of a study visit.

### 7.4 Data Processing and Scoring

Electrocardiograms from all ECG monitoring events are to be presented to the independent reviewer. Participant Number, age and gender are pre-printed on the ECG. The reviewer will make an assessment of each ECG and document the results in the case report form.

ECGs will be examined in each of the following criteria. We have assumed that the HeartStart Intrepid Monitor/Defibrillator runs at a paper speed of 25 mm/s, that is, each second is represented by five large squares.

- a. 1mV calibration, any lead, as the number of large squares
  - A number OR not readable.
- b. Heart rate, as displayed on the ECG
  - A whole number, as beats per minute, OR missing.
- c. Heart rate, as the number of large squares in an RR interval
  - A number OR not readable.
  - Enter one small square as 0.2 large square.
  - Enter a minimum and a maximum if the rhythm is irregular.
- d. Cardiac axis: not readable OR normal OR abnormal.
- e. Rhythm: not readable OR normal OR abnormal.
- f. P wave, any lead: not readable OR normal OR abnormal.
- g. PR interval, any lead: not readable OR normal OR abnormal.
- h. QRS complex, any lead: not readable OR normal OR abnormal.
- i. ST segment, any lead: not readable OR normal OR abnormal.
- j. T wave, any lead: not readable OR normal OR abnormal.
- k. QT interval, any lead: not readable OR normal OR abnormal.
- l. U wave, any lead: not readable OR normal OR abnormal.

Document ID:	CC_TC_ECR_Intrepid 12Lead_2022_11549	Document title: Philips HeartStart Intrepid 12-lead ECG Study – The ICE study Protocol	Classification:	For internal use
Modified:	12SEP2022		Author:	[name]
Version:	2.0		Approver:	Ref to Page 2
Status:	Final		Page:	35 of 51
			Clinical Protocol	

- m. Overall impression ONE OF not interpretable OR normal OR abnormal, but no action required OR abnormal and requires immediate action.

An ECG from the printed patient record is considered to be of diagnostic quality when every part of the waveform in every lead is readable.

SpO2 data and NBP data will be utilized to troubleshoot any 12-lead ECG tracings that are not readable or abnormal.

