Adult criteria apply if the patient age entered is 16 years old or older, or if no age is specified. Pediatric criteria apply if the patient age entered is younger than 16 years of age. Twelve different age ranges are used for the pediatric criteria to account for the rapid changes that occur in the first few days to months of life.

While increasingly detailed and well developed, no automated analysis is completely reliable, and computerized ECG analysis should always be reviewed by a qualified physician.

This study will utilize ECG monitoring via a 12-lead ECG, SpO2 and NBP. The 2015 European Resuscitation Council Guidelines for Advanced Life Support highlights the value of other defibrillation topics (cardioversion, pacing) and physiological monitoring (ECG, end-tidal CO2, SpO2, non-invasive blood pressure) to guide ALS interventions and provide the best cardiac arrest care pre-hospital and in-hospital settings (Soar, 2015).

- ECG monitoring: Monitoring heart rhythm through pads, paddles or ECG electrodes is a standard part of ALS. Motion artifacts prevent reliable heart rhythm assessment during chest compressions forcing rescuers to stop chest compressions to assess the rhythm and preventing early recognition of recurrent VF/pVT.
- SpO2: Pulse oximetry is a common standard of care to establish base line oxygenation and assessing oxygenation while receiving supplemental oxygen. Pulse oximetry is a key element to the initial assessment and treatment of a patient with an arrhythmia, normal readings range from 94% to 100%.
- Non-invasive blood pressure: Blood pressure is a key element to the initial assessment and treatment of a patient with an arrhythmia.

In the Philips HeartStart Intrepid Monitor/Defibrillator the 12-lead ECG is an optional function accessed while in monitor mode. 12-Lead function allows the preview, acquisition printing, copying, and storage of 12-Lead ECGs. In addition, the 12-Lead function provides computerized ECG analysis using one of two configuration options (under 16 years old and over 16 years old) of the DXL Algorithm. A report with measurements and interpretive statements from the analysis is displayed, stored and printed, as configured.

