### 10.1 Sample Size Determination

Each hypothesized endpoint estimates a target proportion of 99% with an expectation to be statistically better than 90%. Using a one-sided exact test, with 80% power and alpha of 0.025, a sample size of 56 evaluable subjects is required.

Both hypothesized endpoints must be met for study success, therefore alpha level adjustments are not necessary to address familywise error.

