### 10.4.2 Analysis of the Primary Endpoints

Endpoint 1A: Obtaining the 12-lead ECG

Endpoint 1B: Diagnostic quality of the 12-lead ECG tracings

A one-sided exact binomial test will be used to assess each of the primary endpoints. Both endpoints must be met for study success.

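### Endpoint 1B is a readability judgement made on the device's own printout, and the plan does not mask the reviewer to the algorithm output that printout shows or may show

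*Combined protocol and SAP*

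**What the plan says.** Section 7.4 sends every tracing to one reader: "Electrocardiograms from all ECG monitoring events are to be presented to the independent reviewer". The reader marks axis, rhythm and each wave, segment and interval as not readable, normal or abnormal. Endpoint 1B follows from those marks: "An ECG from the printed patient record is considered to be of diagnostic quality when every part of the waveform in every lead is readable".

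Two places show what else may be on the page. Item b of the scoring list is "Heart rate, as displayed on the ECG". It stands directly before item c, where the reader works out the rate from the RR interval on the tracing. Section 2.2 says of the 12-lead function: "A report with measurements and interpretive statements from the analysis is displayed, stored and printed, as configured".

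Section 7.4 names participant number, age and gender as pre-printed. It does not say whether the interpretive block is switched on, removed or covered for the read. Section 6.5, on measures to minimize bias, deals only with randomization of electrode age. Section 10.4.5 plans no sensitivity analysis, so there is no masked re-read.

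**The concern.** Section 3 makes validation of the DXL algorithm in this device the study's objective. Endpoint 1B asks a person to judge whether the waveform can be read. If the same sheet carries a printed rate, interval or rhythm statement, that judgement may not rest on the tracing alone. A poorly visible wave may be marked differently when a value for it is printed nearby.

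The stakes come from the decision rule. Section 10.4.2 states: "Both endpoints must be met for study success". As the working shows, 1B tolerates one non-diagnostic result in 56, so a single altered rating can change the outcome of the study. With no masked re-read planned, the data would not reveal such an influence afterwards.

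**Working it through.** **Inputs from the plan.** Section 10.1 gives the null and target proportions, in per cent: "Each hypothesized endpoint estimates a target proportion of 99% with an expectation to be statistically better than 90". The design statement is: "Using a one-sided exact test, with 80% power and alpha of 0.025, a sample size of 56 evaluable subjects is required".

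**Reproducing the sample size.** The one-sample normal approximation gives

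n = [(1.960 × √(0.90 × 0.10) + 0.842 × √(0.99 × 0.01)) / 0.09]² = 55.7, rounded up to 56.

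This matches the plan. By the exact test, the smallest n with at least 80% power is 54 (at least 53 successes, alpha 0.0237, power 0.898). At n = 56 the exact rule requires 55 successes, with attained alpha 0.0198 and power 0.892. The stated 80% is therefore a floor.

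**The decision margin at n = 56.** Assume one yes/no result per participant and all 56 evaluable. The one-sided p-value for x successes is P(X ≥ x | n = 56, p = 0.90).

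| Diagnostic results | Exact p | Lower 95% Clopper-Pearson limit | 1B |
|---|---|---|---|
| 55/56 | 0.0198 | 0.904 | met |
| 54/56 | 0.0719 | 0.877 | not met |

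One participant's result separates the two rows.

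**Illustration of a false pass.** The documents give no rate at which printed output alters a reading, so the fraction f below is an assumption shown over a range. Let true readability be 0.90, the edge of the null, and let f be the fraction of unreadable results called readable. The apparent rate is p = 0.90 + 0.10 × f, and

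P(pass) = p^56 + 56 × p^55 × (1 − p).

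For f = 0.1, p = 0.91 and P(pass) = 0.0051 + 0.0282 = 0.0333.

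| f | Apparent rate p | P(pass 1B) |
|---|---|---|
| 0 | 0.90 | 0.020 |
| 0.1 | 0.91 | 0.033 |
| 0.2 | 0.92 | 0.055 |
| 0.3 | 0.93 | 0.090 |

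The nominal one-sided level is 0.025, so under this assumption f = 0.1 already exceeds it. If printed output pushed readings the other way, the chance of passing would fall.

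**The case against.** The strongest reply is that the exposure is not established. Section 2.2 describes what the device can do, printing depends on configuration, and the study's configuration is not stated. This stands. Only the displayed heart rate is certain to be in view; for the rest, the correct statement is that masking is not specified.

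The reader is also called independent and works through a fixed list. Item c has its own not-readable option, and the criterion covers all leads, so a printed summary statement does not show that a given lead is legible. These features limit any influence but do not take the printed values off the page.

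A reader might infer more than the documents support:

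- **That the reading is biased towards readable.** The direction is an inference. Printed output could push either way.
- **That the reviewer should be blind to the device.** There is one device and no comparator, so only masking to algorithm output is meaningful.
- **That unfavourable ratings get a second look.** Section 7.4 says SpO2 "data and NBP data will be utilized to troubleshoot any 12-lead ECG tracings that are not readable or abnormal". That is troubleshooting; it does not say ratings are revised. An abnormal tracing also still counts as readable, so the trigger includes 1B successes.
- **That a rise from a true 97% to an apparent 99% shows the harm.** The pass probability would go from 0.496 to 0.892, but two thirds of unreadable results would have to flip (3% to 1%). At 97% the alternative is true, so passing is not an error.
- **That a check of DXL against the reader would be contaminated.** No such comparison is planned: section 10.4.2 has two binomial tests, and section 10.4.4 plans no exploratory analyses.

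Finally, section 6.1 has three ECGs per participant and the plan gives no rule for combining them. One altered tracing decides 1B only if it decides that participant's result.

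**Conclusion.** The point holds as a gap in the specification of a primary endpoint. A subjective rating is made from a record that shows at least the device's heart rate and may show DXL measurements and interpretive statements, and the plan does not mask the reviewer to them. Bias is not demonstrated, and neither its direction nor its amount can be taken from the documents.

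The consequence could still be large for a small cause: under one result per participant, a single changed result moves 1B between met and not met. The range of 0.033 to 0.090 for a false pass rests on an assumed f of 0.1 to 0.3 and a true rate of exactly 0.90. It shows how sensitive the rule is and does not estimate what will happen. Since the protection costs little, it should be in place before the first tracing is read. If the study's print configuration already omits the interpretive block, stating so in 7.4 would settle most of the point, leaving the displayed heart rate and the order of scoring.

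**What to change.** Add to section 7.4:

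- The reviewer receives a copy of each printed ECG on which the displayed heart rate and any DXL measurements and interpretive statements are covered. The full printout stays in the participant file.
- The reviewer scores and signs items a and c to m from the covered copy, then uncovers it and enters item b.
- The first signed rating is the value used for endpoint 1B.

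Covering the copy is preferable to switching the output off in the print configuration. Switching it off could remove the heart rate that item b needs and would leave the filed printout incomplete.

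The cost is preparing covered copies and a second, short scoring step. The sample size of 56, the test and the success rule do not change.

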## 7.5 Participant Compensation

Participants who complete the study will be reimbursed \$100 in the form of a gift card for their time and participation in the study. Pro-rated compensation will be provided to individuals whose participation is terminated early for any reason. In that scenario, participants will be reimbursed according to the following schedule:

- Participant signs consent, but is found to be not eligible \$25

## 8. ADVERSE EVENTS AND UNANTICIPATED PROBLEMS

### 8.1 Adverse Events and Serious Adverse Events

#### 8.1.1 Definition of Adverse Events

An AE is any untoward medical occurrence associated with the use of an intervention in humans, whether or not considered intervention-related (21 CFR 312.32 (a)). When an AE is deemed to be related to the study device, it is termed an adverse device event.

##### 1.1.1. Definition of Serious Adverse Events

An AE or suspected adverse reaction is considered serious if, in the view of either the investigator or Sponsor, it results in any of the following outcomes: death, a life-threatening AE, inpatient hospitalization or prolongation of existing hospitalization, a persistent or significant incapacity or substantial disruption of the ability to conduct normal life functions, or a congenital anomaly/birth defect. Important medical events that may not result in death, be life-threatening, or require hospitalization may be considered serious when, based upon appropriate medical judgment, they may jeopardize the participant and may require medical or surgical intervention to prevent one of the outcomes listed in this definition. When a serious AE is deemed to be related to the study device, it is termed a serious adverse device event (SADE).

Document ID:	CC_TC_ECR_Intrepid 12Lead_2022_11549	Document title: Philips HeartStart Intrepid 12-lead ECG Study – The ICE study Protocol	Classification:	For internal use
Modified:	12SEP2022	Clinical Protocol	Author:	[name]
Version:	2.0		Approver:	Ref to Page 2
Status:	Final		Page:	36 of 51

## 8.2 Unanticipated Adverse Device Event

An unanticipated adverse device event (UADE) is defined in 21 CFR Part 812.3(s) as “any serious adverse effect on health or safety or any life-threatening problem or death caused by, or associated with, a device, if that effect, problem, or death was not previously identified in nature, severity, or degree of incidence in the investigational plan or application (including a supplementary plan or application), or any other unanticipated serious problem associated with a device that relates to the rights, safety, or welfare of subjects”.

Other important medical events which may not result in any of the outcomes above, but which may require intervention to prevent one of the outcomes above, may in the opinion of the investigator, be considered a UADE.

## 8.3 Classification of an Adverse Event or Adverse Device Event

### 1.1.2. Severity of Event

All AEs will be assessed by the study clinician using a protocol defined grading system as follows:

- Mild – Events require minimal or no treatment and do not interfere with the participant’s daily activities.
- Moderate – Events result in a low level of inconvenience or concern with the therapeutic measures. Moderate events may cause some interference with functioning.
- Severe – Events interrupt a participant’s usual daily activity and may require systemic drug therapy or other treatment. Severe events are usually potentially life-threatening or incapacitating. Of note, the term “severe” does not necessarily equate to “serious”.

### 8.3.1 Relationship to the Study or Device

All AEs will have their relationship to study procedures and the study device assessed by the clinician who examines and evaluates the participant based on temporal relationship and his/her clinical judgment. The degree of certainty about causality will be graded using the categories below.

- Definitely Related – There is clear evidence to suggest a causal relationship, and other possible contributing factors can be ruled out. The clinical event occurs in a plausible time relationship to study intervention administration and cannot be explained by concurrent disease or other drugs or chemicals. The response to withdrawal of the study intervention should be clinically plausible.
- Probably Related – There is evidence to suggest a causal relationship, and the influence of other factors is unlikely. The clinical event occurs within a reasonable time after

Document ID:	CC_TC_ECR_Intrepid 12Lead_2022_11549	Document title: Philips HeartStart Intrepid 12-lead ECG Study – The ICE study Protocol	Classification:	For internal use
Modified:	12SEP2022	Clinical Protocol	Author:	[name]
Version:	2.0		Approver:	Ref to Page 2
Status:	Final		Page:	37 of 51

administration of the study intervention, is unlikely to be attributed to concurrent disease or other drugs or chemicals.

- Potentially Related – There is some evidence to suggest a causal relationship (e.g., the event occurred within a reasonable time after the application of the electrodes). However, other factors may have contributed to the event (e.g., the participant’s clinical condition, other concomitant events). Although an AE may rate only as “possibly related” soon after discovery, it can be flagged as requiring more information and later be upgraded to “probably related” or “definitely related”, as appropriate.
- Unlikely to be related – A clinical event whose temporal relationship to study intervention administration makes a causal relationship improbable (e.g., the event did not occur within a reasonable time after administration of the study intervention) and in which other drugs or chemicals or underlying disease provides plausible explanations (e.g., the participant’s clinical condition, other concomitant treatments).
- Not Related – The AE is completely independent of study intervention administration, and/or evidence exists that the event is definitely related to another etiology. There must be an alternative, definitive etiology documented by the clinician).

### 8.3.2 Expectedness

The Principal Investigator will be responsible for determining whether an AE is expected or unexpected. An AE will be considered unexpected if the nature, severity, or frequency of the event is not consistent with the risk information previously described for the study intervention.

## 8.4 Adverse Event Assessment and Follow-Up

All AEs including local and systemic reactions not meeting the criteria for a serious adverse event (SAE) will be captured on the appropriate (e)CRF. Information to be collected includes event description, time of onset, clinician’s assessment of severity, relationship to study product (assessed only by those with the training and authority to make a diagnosis), and time of resolution/stabilization of the event. All AEs occurring while on study must be documented appropriately regardless of relationship. All AEs will be followed to adequate resolution.

Any medical condition that is present at the time that the participant is screened will be considered as baseline and not reported as an AE. However, if the study participant’s condition deteriorates at any time during the study, it will be recorded as an AE.

Changes in the severity of an AE will be documented to allow an assessment of the duration of the event at each level of severity to be performed. AEs characterized as intermittent require documentation of onset and duration of each episode.

Document ID:	CC_TC_ECR_Intrepid 12Lead_2022_11549	Document title: Philips HeartStart Intrepid 12-lead ECG Study – The ICE study Protocol  Clinical Protocol	Classification:	For internal use
Modified:	12SEP2022		Author:	[name]
Version:	2.0		Approver:	Ref to Page 2
Status:	Final		Page:	38 of 51

An incidental finding is an anatomical deviation which is found as a result of the 12-lead ECG acquisition with respect to the medical condition of the participant of which they were previously unaware. This study is not for diagnostic purposes, so if incidental health findings are discovered as part of a study the subject will be informed and advised to consult their physician. Further evaluation of such findings shall not be under the purview of the study and the investigators shall not be obliged to bear any further costs. In case of significant incidental finding the study site will have the Principal Investigator repeat the 12-lead ECG with a released device. Any incidental finding and communication to the participant will be noted in the AE form.

## 8.5 Serious Adverse Event or Serious Adverse Device Event Reporting

The study investigator shall complete a SAE or UADE Form and submit to the Sponsor and to the reviewing IRB as soon as possible, but in no event later than 24 hours (for a SAE) or 10 working days (for a UADE) after the investigator first learns of the effect. The Sponsor is responsible for conducting an evaluation of the SAE/UADE and shall report the results of such evaluation to the Food and Drug Administration (FDA) and to the review IRB or 10 working days (for a UADE) after the Sponsor first receives notice of the effect. Thereafter, the Sponsor shall submit such additional reports concerning the effect as FDA requests.

## 8.6 Device Deficiency

All device deficiencies, use or user errors, and equipment failures will be documented. Use or user errors will be captured as part of the source documentation. Device deficiencies and equipment failures will be kept on a separate log. The serial numbers and type of deficiency/failure will be captured. Unanticipated device deficiencies that lead or may lead to an SAE will be reported to the Sponsor within 24 hours of learning of the event.

## 8.7 Unanticipated Problems

### 8.7.1 Definition of Unanticipated Problems

An unanticipated problem (UP) is any incident, experience, or outcome that for which the nature, severity, or frequency is unexpected for the subject population or research activities as described in the current IRB approved protocol, supporting documents, and the consent form.

### 8.7.2 Unanticipated Problem Reporting

The Principal Investigator will submit to the Sponsor and to the reviewing IRB a report of any UADE occurring during an investigation as soon as possible, but in no event later than 10 working

Document ID:	CC_TC_ECR_Intrepid 12Lead_2022_11549	Document title: Philips HeartStart Intrepid 12-lead ECG Study – The ICE study Protocol  Clinical Protocol	Classification:	For internal use
Modified:	12SEP2022		Author:	[name]
Version:	2.0		Approver:	Ref to Page 2
Status:	Final		Page:	39 of 51

days after the investigator first learns of the effect (21 CFR 812.150(a)(1)). Under 812.46(b), the Sponsor shall report the results of such evaluation to the FDA and to all reviewing IRB's and participating investigators within 10 working days after the Sponsor first receives notice of the effect. Thereafter the Sponsor shall submit such additional reports concerning the effect as FDA requests (21 CFR 812.150(b)(1)).

